#### **Study duration**

All subjects will undergo about 40 minutes of ultrasound imaging. Subject who undergo hernia repair will have the same ultrasound imaging done at a standard follow up visit, within six months from the repair itself. Subjects who undergo surgical repair for ventral hernia will have relevant information from their medical records included in the study for up to 1 year.

#### **Resources necessary for human research protection**

Describe research staff and justify that the staff are adequate in number and qualifications to conduct the research. Describe how you will ensure that all staff assisting with the research are adequately informed about the protocol and their research related duties. Please allow adequate time for the researchers to conduct and complete the research. Please confirm that there are adequate facilities for the research.

All members of the study team completed mandatory CITI research training and agree to follow established guidelines to ensure the privacy and respect for study participants. The PI will provide oversight for the study.

## **Characteristics of the Study Population**

#### **Target population**

Up to 25 healthy, adult volunteer subjects and 25 adult subjects seeking surgical repair for ventral hernia between the ages of 20 and 70.

#### **Subjects enrolled by Penn Researchers**

50

#### **Subjects enrolled by Collaborating Researchers**

0

#### **Accrual**

Patients of [name], [name], [name], [name], or [name] seeking surgical repair for ventral hernia will be invited to participate in the study by members of the study team through word of mouth. Healthy volunteers will be invited through word of mouth by

study team members and will be composed for the most part, friends, family, and colleagues. It will be clearly stated that participation is completely voluntary and that their participation is for the purpose of research. Because ultrasound is such a common diagnostic tool, it is anticipated that participants will know what is involved and that it is a painless procedure that takes less than an hour.

#### **Key inclusion criteria**

Adults between the ages of 20 and 70. Healthy volunteer (25) or subject seeking elective ventral hernia repair (25).

#### **Key exclusion criteria**

Pregnant women will not be included in the study. Although ultrasound is a common procedure during pregnancy, our results regarding abdominal wall stiffness as they relate to hernia repair would be compromised by not controlling for other factors that affect the abdominal wall, such as physiologic changes during pregnancy.

#### **Vulnerable Populations**

##### **Children Form**

**Pregnant women (if the study procedures may affect the condition of the pregnant woman or fetus) Form**

**Fetuses and/or Neonates Form**

**Prisoners Form**

**Other**

**None of the above populations are included in the research study**

#### **The following documents are currently attached to this item:**

*There are no documents attached for this item.*

#### **Populations vulnerable to undue influence or coercion**

It will be clearly stated to any healthy volunteers who have an academic or professional relationship with UPENN/UPLS, that participation is voluntary and has no impact on position or care at the health system or academic institution

#### **Subject recruitment**

Patients of [name], [name], [name], [name], or [name] seeking surgical treatment for ventral hernia will be recruited through word of mouth. Healthy volunteers will be invited through word of mouth by study team members and will be composed for the most part, friends, family, and colleagues. It will be clearly stated that participation is completely voluntary and that their participation is for the purpose of research. Because ultrasound is such a common diagnostic tool, it is anticipated that participants will know what is involved and that it is a painless procedure that takes less than an hour.

Will the recruitment plan propose to use any Penn media services (communications, marketing, etc.) for outreach via social media avenues (examples include: Facebook, Twitter, blogging, texting, etc.) or does the study team plan to directly use social media to recruit for the research?

No

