### Primary outcome variable(s)

Sheer wave velocity measurements in the abdominal wall.

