## Background

Significance of hernia and magnitude of the problem: Two million abdominal surgeries are performed annually in the United States, and ventral hernia (VH) is among the most common and serious complications(1, 2). The incidence of VH is approximately 13%(3), but as high as 70% in high-risk populations(1, 4-8). Despite improving surgical treatment strategies and mesh technology, long-term success rates of VH repair remain unacceptably low. The 348,000 VH repairs performed in 2006 cost over \$3 billion (2). As a result of recurrence and morbidity, a disproportionately small subset (15%) of patients consumes more than 50% of expenditures(9), and become caught in the vicious cycle of hernia recurrence and morbidity. Failed repairs generate un-closable midline defects that require mesh bridging, meaning that native fascia cannot be closed and that mesh is bridged across the fascia. Bridging is a relevant and clinically meaningful outcome that occurs during the repair and has significant implications since these repairs fail in 44 to 100% of cases and are associated with significant cost (8, 10-13). Patients suffering from recurring hernia experience deterioration in quality- of-life, significant disability, and dysfunction; if un-closable defects can be identified using a point-of- care technology peri-operative decision-making could be substantially improved. Role of imaging in hernia care: There are currently no reliable data, standard imaging modalities, or guidelines available to predict successful fascial closure in hernia repair, which represents a substantial gap in knowledge and barrier to progress (4, 14-16). Surgeons are unable to adequately counsel patients and preoperatively plan complex VH repairs, which presents a clinical dilemma. The current state of hernia repair relies heavily on clinical evaluation of patients, which, as stated, is ultimately a poor predictor of patient outcome going into surgery for hernia repair. Additionally, there is a dearth of data regarding the use of various imaging modalities to diagnose and predict hernia outcomes of any kind. As of today, the only

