real time visualization and characterization of changes in the biomechanical properties of diseased musculoskeletal tissues. We hypothesize that ARFI-SWV US can be used preoperatively to measure the stiffness in the lateral abdominal wall as an estimation for mobility during hernia repair. Demonstrating the utility of a cheap, point-of-care test for preoperatively evaluating hernia severity will prove to be a valuable, novel tool in surgical assessment of ventral hernia patients. Aim 2. To perform a prospective pilot ARFI-SWV US assessment of abdominal wall characteristics that predicts success of midline fascial re-approximation in hernia patients. A prospective comparative analysis of preoperative ARFI- SWV US exams in patients undergoing hernia repair (N=25) will be performed. We hypothesize that fibrosis and other identifiable mechanical characteristics of the abdominal wall musculature can predict ability to close fascia in VH patients. Preoperative identification of ultrasound features characteristic of severe hernia defects can be used to predict which hernias will be un-closable, resulting in poorer outcomes. The study proposes to compare ultrasound images and associated shear wave velocity measurements between healthy subjects and subjects undergoing surgical repair for ventral hernia. We will compare up to 25 healthy volunteers with up to 25 ventral hernia subjects. Any female patients of child-bearing age will be asked to take a urine pregnancy test prior to being included in the study at the time of consent. Subjects with ventral hernia will undergo imaging no earlier than two weeks prior to elective hernia repair and within six months following repair at a standard followup visit. Medical information related to their hernia or hernia repair from these subjects will remain available for analysis for the duration of the study. Statistical analysis will determine if there is a significant difference in the abdominal wall stiffness, represented by the ultrasound shear wave velocity measurements, between the healthy subjects and the subjects with ventral hernia. Further analysis will determine if there is any statistically significant relationship between abdominal wall stiffness of subjects with ventral hernia and surgical outcomes, including bridged repairs, as well as any change in abdominal wall stiffness following ventral hernia repair.

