### **Analysis Plan**

Analysis will include comparing shear wave velocity measurements between healthy subjects and subjects with ventral hernia as well as correlating these measurements with the surgical outcome/data among patients with ventral hernia. Further, we will compare the measurements taken in subjects who underwent hernia repair before and after the hernia repair.

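### Controls come mostly from the study team's own circle, and the plan neither records volunteers' body size or surgical history nor adjusts the healthy-versus-hernia comparison for any covariate

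*Combined protocol and SAP*

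**What the plan says.** The primary outcome is "Sheer wave velocity measurements in the abdominal wall". Two places describe the between-group use of it. Design: "Statistical analysis will determine if there is a significant difference in the abdominal wall stiffness" between healthy and hernia subjects. Analysis Plan, first item: "Analysis will include comparing shear wave velocity measurements between healthy subjects and subjects with ventral hernia". Neither names a model, matching, stratification or a covariate.

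The groups have different sources. Under Accrual and Subject recruitment, volunteers are approached by word of mouth by "study team members and will be composed for the most part, friends, family, and colleagues". The cases are patients of named surgeons; Target population describes them as "25 adult subjects seeking surgical repair for ventral hernia between the ages of 20 and 70". Apart from the age range, the only shared restriction is the pregnancy exclusion. Its rationale, under Key exclusion criteria, is that results would be "compromised by not controlling for other factors that affect the abdominal wall".

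Procedures lists ultrasound measurements for everyone: muscle thickness, colour Doppler and shear wave readings. It lists no height, weight or surgical history for volunteers, who attend once. Chart review is described only for subjects who have a repair.

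**The concern.** The two groups are not randomised and are recruited by different routes, so they may differ in more than hernia. If they differ in a factor that is also related to shear wave velocity, the unadjusted test attributes that difference to hernia status. Depending on direction, this can create an apparent stiffness difference or hide a real one.

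The protocol accepts this principle when it excludes pregnancy, but applies it to nothing else. It also points to one likely difference itself: the Background, speaking of abdominal surgery, says "ventral hernia (VH) is among the most common and serious complications". Prior surgery may therefore be common among cases, and it is not listed for controls.

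Timing matters. With a single volunteer visit and no chart review for volunteers, body size and surgical history that are not recorded that day are hard to recover.

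**Working it through.** The documents state no alpha, power, effect size or SD, so there is no figure of the plan's own to reproduce. The calculation below shows only how much an unadjusted imbalance could matter.

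**From the documents:** up to 25 per group, not randomised, no adjustment.

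**Assumed:** two-sided 5% test; 25 per group reached; one covariate with within-group correlation r = 0.1 to 0.5 with shear wave velocity; group means of that covariate D = 0.25, 0.5 or 1 SD apart.

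**Step 1. Bias.** The spurious difference, in SDs of shear wave velocity, is r × D. The non-centrality of the t-test is r × D × √(25/2) = 3.54 × r × D, with 48 degrees of freedom. For r = 0.3 and D = 1, the bias is 0.30 SD and the non-centrality is 1.06.

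**Step 2. False positives with no hernia effect (non-central t):**

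| Imbalance D | r = 0.1 | 0.2 | 0.3 | 0.4 | 0.5 |
|---|---|---|---|---|---|
| 0.25 SD | 5.1% | 5.3% | 5.8% | 6.4% | 7.2% |
| 0.5 SD | 5.3% | 6.4% | 8.1% | 10.7% | 13.9% |
| 1 SD | 6.4% | 10.7% | 18.0% | 28.3% | 41.0% |

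Simulation (20,000 runs) gave 18.3% at r = 0.3, D = 1 and 41.0% at r = 0.5, D = 1.

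**Step 3. Bias against a real effect.** An unbiased 25 v 25 test has 80% power at d = 0.809. If the bias opposes this, the net difference is 0.809 − r × D. For r = 0.3 and D = 1 it is 0.509, and power is 42%. Over r = 0.1 to 0.5, power is 75% to 49% at D = 0.5 and 69% to 19% at D = 1.

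**Step 4. What adjustment achieves.** In a linear model with group and the covariate, the variance of the group effect is multiplied by (1 + D²/4)(1 − r²).

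- If the covariate is the sole confounder, well measured and linear, simulated false positives return to about 5%.
- At r = 0.3, D = 1 the multiplier is 1.25 × 0.91 = 1.1375. By the normal approximation, the difference detectable with 80% power moves from 0.792 to 0.792 × √1.1375 = 0.845 SD.

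**Step 5. What adjustment leaves.** With two factors, each r = 0.3 and 1 SD apart, false positives are about 55% with neither adjusted and about 16% with one adjusted.

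**Step 6. Power of a three-covariate model.** With one covariate prognostic, d = 0.81 and r = 0.3, simulated power is about 81% if the groups are balanced, 72% if the prognostic covariate is 1 SD apart and 57% if all three are. Over r = 0.1 to 0.5 these become 78–88%, 68–80% and 54–65%.

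**The case against.** This is a pilot, no imbalance has been shown, and no section links shear wave velocity to age, sex or body size. Friends, family and colleagues may well span the age range. The choice of age, sex and BMI rests on convention, and the model leaves out prior surgery, the factor the protocol most clearly points to. Adjustment can also cost power in a study this small.

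Much of this stands as a limit on the claim. The range of 5% to 41% shows that confounding can matter, not that it does here. Prior surgery is left out of the model because it is likely to be tied closely to hernia status, so a model could not cleanly separate the two. That is a reason for recording it and for cautious wording. The pilot label does not remove the point, because Design still commits to a significance test of the group difference.

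Stronger readings that a reader might infer are not supported:

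- *No adjustment for age or sex would be possible.* Age is needed to apply the 20 to 70 limit, and sex to offer the pregnancy test. For these two the gap is prespecification only.
- *The comparison is biased.* Recruitment source alone does not show this.
- *Both sections commit to a significance test, or the healthy comparison is the leading aim.* Only Design mentions significance. Neither numbered aim names the healthy comparison, and Design gives the within-hernia Aim 2 before it.
- *The whole study is undermined.* The before/after and surgical-outcome analyses do not use the volunteers.

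Whether controls are confirmed to have normal abdominal wall anatomy, as Overall objectives wants, is a separate question on which this point does not depend.

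**Conclusion.** The concern holds as an omission, with high confidence. The between-group comparison of the primary outcome has no matching or adjustment. As written, the plan could not correct later for a difference in body size or surgical history, because neither is listed for volunteers. For age and sex, correction is possible but unplanned.

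The size and direction of any bias are unknown. Mild imbalance does little harm: at 0.25 SD false positives stay between 5% and 7%. At 1 SD they run from 6% to 41%. These figures rest wholly on the assumed r and D.

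The point is worth fixing because the remedy is cheap at the first imaging visit and hard to apply afterwards.

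**What to change.** 1. In Procedures, record age, sex, height, weight and prior abdominal surgery in both groups at the first imaging visit, and report balance between the groups.
2. In the Analysis Plan, prespecify a linear model of one shear wave velocity value per subject on group, adjusted for age, sex and BMI, reported with the unadjusted comparison.
3. Describe the result as an association. Adjustment reduces confounding from the measured factors, but prior surgery and unmeasured factors may remain.

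The cost is one height and weight measurement and a brief history per subject, plus short wording changes. No extra subjects are needed. The statistical price is some loss of precision if the groups differ strongly, down to about 57% power in the r = 0.3 case with all three covariates 1 SD apart. With balanced groups there is essentially none (about 81%, against 80% unadjusted).

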#### **The following documents are currently attached to this item:**

*There are no documents attached for this item.*

#### **Subject compensation\***

Will subjects be financially compensated for their participation?

No

#### **The following documents are currently attached to this item:**

*There are no documents attached for this item.*

**If there is subject compensation, provide the schedule for compensation per study visit or session and total amount for entire participation, either as text or separate document**

na

## **Study Procedures**

### **Suicidal Ideation and Behavior**

Does this research qualify as a clinical investigation that will utilize a test article (ie- drug or biological) which may carry a potential for central nervous system (CNS) effect(s)?

No

### **Procedures**

First Encounter: After informed consent is obtained by a member of the study team, each healthy volunteer and patient seeking ventral hernia repair will undergo ultrasound imaging for about 40 minutes as per the procedure outlined below. Any women of childbearing age will be asked to take a urine pregnancy test prior to enrollment. The ultrasound machine is the Siemens Acuson S3000 and our protocol is within its FDA approved label. The ultrasound imaging will focus on the abdominal wall and avoid areas with the potential for incidental findings, such as the gall bladder. Ultrasound Protocol:

1) Subject will be relaxed with shallow breathing and arm crossing over the chest. 2) Ultrasound transducer pressure will be minimal. 3) Ultrasound transducer will be perpendicular to the abdominal wall. 4) Transducer to be used: Linear or curved. 5) Grayscale Parameters: Abdominal wall musculature thickness in lateral mid abdomen (internal oblique, external oblique and transverse abdominis and rectus abdominis muscles. 6) Measurements will be in orthogonal planes 7) Repeat same procedure on the contra-lateral side 8) Color Doppler: Color Doppler image with optimum sensitivity along with grayscale images. Shear Wave Measurements: 1) A total of 10 measurements using quantification mode, with ROI placed within the musculature in lateral mid abdomen 2) Elastography using Color Map generation (two times in same region) within the musculature in lateral mid abdomen 3) Same measurements to be obtained for rectus abdominis muscle 4) Same measurements to be obtained for contralateral side Healthy volunteers will be thanked for their participation and subjects seeking ventral hernia repair return to their day and will eventually undergo standard treatment they would have otherwise done if they were not included in the study. Subjects who undergo ventral hernia repair will have followup care as per their standard treatment and information obtained through chart review regarding their medical course and surgical outcome/data (such as hernia defect size, if repair required components separation or mesh, complications ) will be included in the study analysis. Follow up Encounter: Subject who underwent surgical repair will also be asked to repeat the exact same ultrasound evaluation at a standard follow up visit with their surgeon within six months of their hernia repair.

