### Secondary outcome variable(s)

Identification of any association between muscular elasticity/stiffness of the abdominal and surgical data/outcomes of the hernia repair.

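### No masking of chart abstraction to shear wave velocity is described, so the coding of borderline complications could bias the secondary stiffness-complication association

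*Combined protocol and SAP*

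**What the plan says.** The only secondary outcome is "Identification of any association between muscular elasticity/stiffness of the abdominal and surgical data/outcomes of the hernia repair". Under Procedures, the outcome side comes from "information obtained through chart review regarding their medical course and surgical outcome/data", with examples given as "such as hernia defect size, if repair required components separation or mesh, complications". Under Study duration, patients who have repair "will have relevant information from their medical records included in the study for up to 1 year". The Analysis Plan covers this link in one clause: "correlating these measurements with the surgical outcome/data among patients with ventral hernia".

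On timing, the Design section places the first scan in the two weeks before repair, so a velocity value exists for each patient before any outcome can be coded. On direction, the Background says that muscle fibrosis impedes closure. The Design section states: "We hypothesize that fibrosis and other identifiable mechanical characteristics of the abdominal wall musculature can predict ability to close fascia in VH patients". It adds that un-closable hernias do worse.

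The protocol does not say who abstracts the chart, what that person may see, what counts as a complication, how complications are graded, or when the 1-year window starts.

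**The concern.** Abstraction is a separate step at which bias can enter. Even if the scan is read without prejudice and the operation is unaffected by the scan, someone must later decide whether, for example, a minor wound problem counts as a complication. If that person knows the wall was stiff and expects stiff walls to do badly, doubtful cases can drift towards an event in stiff patients and away from it in compliant ones. That would produce, or inflate, an association between stiffness and complications. With up to 25 hernia patients, a few reclassified cases can matter. The team intends this pilot as the basis for later studies of a prognostic tool, so a spurious association could be carried forward.

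**Working it through.** The documents state no test, alpha, complication rate or sample-size derivation for this analysis, so there is no figure of the plan's own to reproduce. The check has two parts.

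**1. Which outcomes leave room for coding?**

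| Item | Where named | Room for an abstractor's judgement |
|---|---|---|
| Defect size, components separation, mesh | Procedures | Little: operative record |
| Bridged repair | Design | Little: fixed in the operating room (Background: "Bridging is a relevant and clinically meaningful outcome that occurs during the repair") |
| Complications | Procedures | Yes: no definition, grade or time window |
| Medical course | Procedures | Yes: no content specified |

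The exposure is therefore limited to the last two rows.

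**2. How large could the bias be?**

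Input from the documents: n = 25 hernia patients, the maximum.

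Assumed inputs:
- no true association, with velocity normally distributed;
- clear complications in 10, 20 or 30% of patients;
- borderline cases in a further 5, 10, 20 or 30%;
- a two-sided t-test of velocity by coded complication at alpha 0.05.

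Three coding rules were applied to borderline cases:
- *Masked*: coin flip.
- *75:25 lean*: half are coded by velocity (event if above the median) and half by coin flip. Above the median, P(event) = 0.5 × 1 + 0.5 × 0.5 = 0.75. Below it, P(event) = 0.5 × 0 + 0.5 × 0.5 = 0.25.
- *Full lean*: every borderline case is coded by velocity.

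Each setting had 6,000 runs. Runs with fewer than two patients in either outcome group counted as non-significant. The simulation standard error at a 5% rate is √(0.05 × 0.95 / 6,000) = 0.0028, or about 0.3 percentage points.

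False-positive rate (%):

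| Clear | Borderline (expected cases = 25 × share) | Masked | 75:25 lean | Full lean |
|---|---|---|---|---|
| 10% | 5% (1.25) | 4.6 | 4.1 | 5.1 |
| 10% | 10% (2.5) | 4.5 | 5.0 | 7.4 |
| 10% | 20% (5) | 5.0 | 7.8 | 16.5 |
| 10% | 30% (7.5) | 5.3 | 9.9 | 27.6 |
| 20% | 5% (1.25) | 5.8 | 5.0 | 5.5 |
| 20% | 10% (2.5) | 5.1 | 5.1 | 7.0 |
| 20% | 20% (5) | 4.8 | 7.0 | 13.8 |
| 20% | 30% (7.5) | 5.1 | 9.6 | 24.6 |
| 30% | 5% (1.25) | 5.7 | 5.0 | 5.1 |
| 30% | 10% (2.5) | 5.0 | 5.4 | 6.4 |
| 30% | 20% (5) | 5.4 | 6.8 | 12.8 |
| 30% | 30% (7.5) | 4.8 | 9.5 | 24.0 |

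Masked coding stays near 5% throughout (4.5-5.8%). With 10-30% borderline cases, the 75:25 lean gives 5.0-9.9%. Full lean gives 6.4-7.4% at 10% borderline, 12.8-16.5% at 20%, and 24.0-27.6% at 30%. At 5% borderline, about one patient, there is no visible effect under any rule.

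**The case against.** Much of the case on the other side stands.

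- *A reader might infer that the abstractor works with the velocity results in view.* The documents do not say so. They are silent on who abstracts and what that person sees. The Data confidentiality section does not settle it: it mentions access privileges, which are compatible with restricted access. It also lists items that do not fit this study (web-based surveys, audio or video recordings), so it reads like a form whose tick marks were lost. The supportable statement is that no masking is described.
- *A reader might extend the point to all surgical outcomes.* That goes too far. Bridging, the outcome the aims stress, and the listed operative items are settled in the operating room. Whether the surgeon knows the velocity beforehand is a different question, which the documents also leave open.
- *A reader might think the bias could never be found afterwards.* It could. The chart remains, and a masked person can re-abstract it and check agreement.
- *The direction is only partly stated.* The explicit hypothesis concerns fascial closure, and the secondary outcome is any association. Worse outcomes appear only as a consequence of un-closable hernias. No hypothesis that stiffness predicts complications is written down.
- *This is a pilot, and the affected analysis is secondary.* Neither the hernia-versus-healthy comparison nor the before-and-after comparison uses chart-coded outcomes.

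What remains is that complications and medical course do need judgement, velocity does exist first, and nothing in the plan separates the two.

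**Conclusion.** The point holds as an inexpensive improvement to the secondary analysis. It is not a flaw that threatens the study. The route for bias is confined to complications and medical course.

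Under a moderate lean the false-positive rate rises from 5% to at most about 10%. To reach about 13-28%, some 5 to 7.5 of 25 cases must be borderline and every one must be coded by velocity. The simulation therefore shows that a spurious association could arise, and does not show that one will. The complication rate, borderline share, strength of lean, alpha and choice of test are all assumptions. Confidence that the bias would be material is low.

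**What to change.** In Procedures, state that complications and medical course will be abstracted against a written list, with definitions and a time window, by an existing team member who did not perform the scan and does not see the velocity values. State also that these REDCap fields will be locked before velocity is merged by study ID.

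The section on resources gives no team size or roles, so it is not certain that such a person exists. If not, complete and lock the abstraction before the velocity file is opened, or report the complication association as unmasked and exploratory.

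The cost is a short addition to the protocol, a one-off list, and a data-access setting in the REDCap database that the plan already provides. No visits, patients or procedures are added. The downside is that velocity must be withheld from one team member until lock, which, with up to 1 year of chart data, comes late for the last patients. The fix does not govern what treating clinicians write in the chart, so it removes bias at abstraction only.

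### Hernia defect size is listed with the surgical outcome data and never adjusted for, so the plan cannot show whether stiffness says anything about fascial closure beyond the size of the gap

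*Combined protocol and SAP*

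**What the plan says.** The protocol and analysis plan are one document.

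- Study Design, Design (Aim 2) hypothesises that "fibrosis and other identifiable mechanical characteristics of the abdominal wall musculature can predict ability to close fascia in VH patients", and adds: "Preoperative identification of ultrasound features characteristic of severe hernia defects can be used to predict which hernias will be un-closable". It plans a test of the relationship between stiffness and "surgical outcomes, including bridged repairs".
- Secondary outcome variable(s) is worded broadly: "Identification of any association between muscular elasticity/stiffness of the abdominal and surgical data/outcomes of the hernia repair".
- Study Procedures, Procedures describes the chart review: "surgical outcome/data (such as hernia defect size, if repair required components separation or mesh, complications ) will be included in the study analysis". Defect size is not among the ultrasound measurements in that section; it appears only as chart data.
- Analysis Plan gives the whole method for this question: "correlating these measurements with the surgical outcome/data among patients with ventral hernia".

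No section names a covariate, an adjusted or stratified analysis, or a comparison of the scan with defect size.

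**The concern.** Defect size is a property of the hernia before surgery, not a result of the repair. It may also be linked to both sides of the Aim 2 association. A wider gap is plausibly harder to close; this is a premise of the review, not a figure from the documents. The Background says that unloaded abdominal muscle atrophies and becomes fibrotic, and that fibrosis impedes closure. A larger hernia could therefore go with a stiffer wall. Aim 2 itself expects the scan to pick up features of severe defects.

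If velocity is associated with bridging only because both follow defect size, a surgeon who already knows the size of the gap learns nothing more from the scan. The Background and Design sections promote the scan as a point-of-care aid for identifying hernias that cannot be closed, so value beyond defect size is the natural next question. The planned correlations cannot answer it. Listing defect size with the surgical results also blurs two findings: a correlation with size describes the hernia, while a correlation with bridging concerns the operation.

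**Working it through.** **Nothing to reproduce.** The documents give no alpha, power, effect size, SD, bridging rate or link strength for this analysis. They speak only of significance. What follows is an illustration.

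**Input from the documents.** At most 25 hernia patients (Design, Aim 2).

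**Assumptions.** Two-sided alpha 0.05; 20% or 30% bridged, that is 25 × 0.20 = 5 or 25 × 0.30 = 7.5 patients; stiffness–size correlation r of 0.3, 0.5 or 0.7; odds of bridging multiplied by 2 or 4 per SD of defect size; no effect of stiffness on bridging once size is known.

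**Model.** Size W ~ N(0,1). Stiffness S = rW + √(1 − r²)·e, with e ~ N(0,1). logit P(bridged) = a + ln(2 or 4)·W, with a set to give the assumed rate. At least two patients are required in each of the bridged and closed groups.

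**Tests.** The unadjusted test compares velocity between bridged and closed patients, which is equivalent to testing their correlation r(SB). The adjusted test uses the partial correlation

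[r(SB) − r(SW)·r(WB)] / √{[1 − r(SW)²][1 − r(WB)²]}

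The critical value is t/√(df + t²):
- unadjusted, df = 23: 2.069/√(23 + 2.069²) = 0.396
- adjusted, df = 22: 2.074/√(22 + 2.074²) = 0.404

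**Share of simulated trials with a significant result:**

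| Odds per SD of size | r = 0.3 | r = 0.5 | r = 0.7 |
|---|---|---|---|
| ×2, unadjusted | 6–7% | 9–10% | 14–17% |
| ×4, unadjusted | 9–11% | 17–21% | 31–39% |
| Either, size held fixed | about 5% | about 5% | about 5% |

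**Check with a different model.** Here bridging comes from a latent normal variable, with 20% or 40% bridged. The unadjusted test was significant in about 6% of trials when both links with size are 0.3, 13–16% when both are 0.5, and 40–50% when both are 0.7. The adjusted test stayed at 4.7–5.3%. The pattern is the same: small with weak links, large with strong ones.

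**What adjustment costs.** The lost degree of freedom is minor (0.396 to 0.404). The overlap between stiffness and size matters more. With a real independent effect of stiffness (assumed odds ×3 per SD) added to the ×4 model, the adjusted test was significant in only about 17–39% of trials, and least often at r = 0.7.

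**The case against.** The strongest reply is that the plan promises association and prediction, not independence from defect size. A marker that works only because it follows defect size still predicts. This stands, and it rules out two stronger readings that a reader might infer.

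- *That the planned correlation cannot show prediction at all.* It can show crude prediction. What it cannot show is information beyond size.
- *That the simulated rates are false positives of the plan's own test.* In those simulations stiffness and bridging really are associated, through size. The rejections are errors only for a size-independent link, which the documents do not claim.

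Three further replies stand in part.

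- The wording covers data as well as outcomes, so defect size may have been meant as description. No composite is formed, and where the Design section names an outcome of this kind it names bridged repairs. Even so, the only use the plan gives defect size is as one of the items to correlate with stiffness.
- A stiffness–size correlation is not worthless. Aim 1 proposes the scan for assessing hernia severity, and such a correlation bears on that.
- The link strengths are assumed. The Background itself says reliable data for predicting closure are lacking.

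It might also seem natural to allow a claim of prediction only if the adjusted test is significant. With 25 patients that rule would miss a real independent effect in most trials, as the last calculation shows. Non-significance would not be evidence that the scan adds nothing.

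**Conclusion.** The point holds in a limited form. Defect size has no baseline role in the plan, and the only planned analysis of stiffness against surgical findings is unadjusted. The study as written could report crude prediction of closure, but could not say whether the scan adds to defect size.

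How far a reader could be misled depends on links that the documents do not give. Under the assumptions above, a chance of about 5% of wrongly inferring a size-independent link becomes about 6–17% if the odds of bridging double per SD of size, and about 9–39% if they quadruple. With weak links the problem is slight.

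The documents do not support saying that the secondary analysis is invalid or that its error rate is inflated for the association it sets out to test. This is a secondary analysis in a pilot, and the primary comparison with healthy volunteers is unaffected. The change is worth making, somewhere between optional and recommended.

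**What to change.** In Procedures and Analysis Plan:

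1. Take defect size out of the surgical outcome list and name it as a baseline characteristic. State which dimension is used, its source, and whether it is measured before or during surgery.
2. Report the Aim 2 association between stiffness and bridging twice: unadjusted, as crude prediction, and adjusted for defect size. One form suited to few bridged patients is a linear regression of velocity on bridged/closed plus defect size. Give confidence intervals for both and label them exploratory.
3. Report the stiffness–size correlation separately, as a description of hernia severity.
4. Do not make a statement about prediction depend on significance of the adjusted test. Base only statements about value beyond defect size on the adjusted estimate and its interval.

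The cost is mainly wording, because defect size is already taken from the chart, plus the work of fixing how and when it is measured. The adjusted estimate will be imprecise: about 5 to 8 bridged patients at the assumed rates, and less able to detect a real effect the more closely stiffness and size are correlated. The report should say so.
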